6.3. Exploratory Endpoints

Exploratory endpoints include:

- Cellular immune responses to chikungunya antigens: PBMCs will be collected on Days 1, 8, 29, 57 and 182 in order to determine the nature and stability of the cellular immune response to PXVX0317.
- Humoral immune responses at other time points, to other pathogens (including EEEV and WEEV) and using other thresholds than those specified above may be performed in selected subjects.

6.3.1. Analysis Methods for Exploratory Endpoints

As part of an exploratory analysis, the chikungunya-specific cellular immune (IFN-g ELISpot) response of prior alpha subjects will be compared to that of naïve alpha subjects. Assay results will be reported as the number of spot-forming cells per 1 million PBMC (SFC / 10^6 PBMC). The sample size, mean, median, 25th and 75th percentiles, and minimum and maximum SFC / 10^6 PBMC will be summarized for each study arm at each visit. A p-value from a comparison of the two groups using a Wilcoxon Rank Sum test will be provided for each visit.

The percentage of subjects achieving specified thresholds (2, 4, 8, and 16 fold increase over Day 1 in SFC / 10^6 PBMC), and associated Wilson 95% CIs, will be summarized at each visit. The groups will be compared by pairwise Fisher's exact tests on the percentage achieving each threshold.

Analogous methods will be used to summarize VEEV-specific IFN-g.

Any exploratory humoral antibody data will be summarized using similar methods as those used to summarize the secondary antibody endpoints. All exploratory analyses will be based on the IEP and only valid sample results will be included in the analyses.

6.4. Immunogenicity Subgroup Analysis

Subgroup analyses by race group – white or non-white – and gender will be conducted for the following endpoints:

- Anti-CHIKV neutralizing antibodies, determined by luciferase-based assay (NT80), in prior alpha subjects vs. naïve alpha subjects, assessed by
 - Seroconversion rates on Days 8, 22, 29, 57 and 182
 - GMT and GMR on Days 1, 8, 22, 29, 57 and 182
 - The proportion of subjects with titers of at least 40, 100, 160 or 640 on Days 1, 8, 22, 29, 57 and 18

Statistics and p-values for all sub-group analyses will be calculated using the same methods as described for the endpoint except for GMT and GMR analyses. The mean of the \log_{10} -transformed titers will be calculated and then exponentiated to convert to the non-transformed scale to estimate the GMT. 95% CIs for the GMT will be calculated by constructing a *t*-interval for the mean of the transformed titers and then back-transformed. The GMR of the prior alpha group to the naïve alpha group, and its 95% CI, will be calculated by taking the difference between groups in log-transformed space and then exponentiating the difference. *T*-tests will be used to compare \log_{10} -transformed titer data between the prior alpha and naïve alpha subjects. The median, minimum and maximum will be summarized based on the non-transformed scale.

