9.6 Immunogenicity Analysis

All tests will be carried out at a 2-sided significance level of 0.05 and no adjustment for multiplicity will be applied.

Seroconversion Analysis:

The primary immunogenicity analysis will compare prior alphavirus vaccine recipients to alphavirus-naïve controls on the proportion in each group who seroconvert by anti-CHIKV neutralizing antibody at Day 22. Seroconversion is defined as a 4-fold or greater rise over baseline in anti-CHIKV neutralizing antibodies as assessed by a luciferase-based assay.

Specifically, we will test the hypotheses:

$$H_0: P_1 = P_2 \text{ vs. } H_1: P_1 \neq P_2$$

where P_1 and P_2 denote the proportion of subjects who seroconvert in the prior alphavirus vaccine recipients and the alphavirus-naïve controls, respectively.

The significance of the comparison of the pre-exposure groups will be assessed using a Fisher's exact test. The percentage who seroconvert in each group will be presented along with its 95% CI calculated using the Wilson method. A sensitivity analysis of the comparison will be performed using a logistic regression model that incorporates age, gender, and baseline titer as potential predictive factors. Fisher's test comparing seroconversion rates at other time points may also be performed. Similar analyses of the proportion who seroconvert will be conducted on Days 8, 29, 57 and 182 for anti-CHIKV neutralizing antibody and on Days 22 and 29 for total anti-CHIKV, total anti-VEEV and neutralizing anti-VEEV antibodies (secondary endpoints).

Threshold analyses:

The percentage of subjects achieving specified thresholds (e.g., ≥ 40 , 160, and 640 anti-CHIKV antibody titers), and associated Wilson 95% CIs, will also be calculated for Days 1, 8, 22, 29, 57 and 182 for neutralizing antibody and at Days 1, 22 and 29 for total anti-CHIKV, total anti-VEEV and neutralizing anti-VEEV antibodies (secondary end-points). The groups will be compared by pairwise Fisher's exact tests on the percentage achieving each threshold.

GMT analyses:

For the secondary comparisons based on GMT, the hypotheses tested will be

$$H_0: \mu_1 = \mu_2 \text{ vs. } H_1: \mu_1 \neq \mu_2$$

where μ_1 and μ_2 denote the GMT for the prior alphavirus vaccine recipients and the alphavirus-naïve controls, respectively.

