6.1.1. Analysis Methods for Primary Immunogenicity Endpoint

The primary immunogenicity analysis will compare the proportion of prior alpha subjects to the proportion of naïve alpha subjects with seroresponse by anti-CHIKV neutralizing antibody at Day 22. The significance of the comparison of the two groups will be assessed using a Fisher's exact test. The percentage with seroresponse in each group will be presented along with a 95% CI calculated using the Wilson method (Agresti 1998). The difference and a 95% CI for this difference calculated based on Newcombe hybrid score method will also be presented. The primary immunogenicity analysis will be performed on both the IEP and mITT population.

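### SAP 6.4 tests the arms separately within each race and gender level and plans no interaction, so it cannot show whether the arm effect differs by race or gender

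*SAP*

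**What the plan says.** SAP 6.4 sets the scope: "Subgroup analyses by race group – white or non-white – and gender will be conducted for the following endpoints". The endpoints all come from the CHIKV luciferase neutralization assay:

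- seroresponse at the five post-vaccination visits with serum
- geometric mean titers and their ratio at those five visits and at Day 1
- four titer thresholds at the same six visits, worded as "The proportion of subjects with titers of at least 40, 100, 160 or 640 on Days 1, 8, 22, 29, 57 and 18" (the last day is evidently Day 182; the count does not change)

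On testing, it says "Statistics and p-values for all sub-group analyses will be calculated using the same methods as described for the endpoint", with an exception for GMT and GMR. For seroresponse the endpoint method is the one in SAP 6.1.1: "The significance of the comparison of the two groups will be assessed using a Fisher's exact test". SAP 6.2.1 also uses Fisher's test at each titer threshold. For subgroup GMTs, SAP 6.4 replaces the model with raw log10 means and t-tests between arms.

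Protocol 9.6 adds: "All tests will be carried out at a 2-sided significance level of 0.05 and no adjustment for multiplicity will be applied".

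The main GMT model for the evaluable population (SAP 6.2.1) contains arm, age and gender as main effects only. Neither document contains an arm-by-subgroup term. Protocol 9.6 foresaw only summaries by age and gender. The SAP section on changes to the protocol's methods (section 8) does not mention the move to race and gender with p-values.

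**The concern.** A subgroup analysis is meant to show whether the arm difference varies between levels. Separate tests within levels do not answer that. A p-value below 0.05 in women and above it in men can arise when the effect is identical in both, or when there is none. Only a direct contrast of the two arm effects addresses the question, and none is planned.

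The question is not foreign to this trial. Protocol 9.3 justifies matching partly on the ground that age and gender matter for interference between alphaviruses. An isolated small p-value in one level could therefore be taken as evidence of interference specific to that level.

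A second, smaller point concerns the race-level GMRs. They drop the age and gender adjustment of the main model, so they do not line up with the overall GMR.

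**Working it through.** **1. The plan's nearest own figure.** The documents give no figure for the subgroup analyses. The sample-size statement is 80% power for 65% versus 95% seroconversion with 30 per arm. Exact enumeration of Fisher's test at two-sided 0.05 gives 78.8%, which agrees with the stated 80%. The same method reproduces Table 3 (for example 89.3% against the printed 89% for 30 per arm at 60%).

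**2. What separate tests can show.** For the same 65% versus 95%, exact power is 58.9% at 20 per arm, 39.6% at 15 and 15.7% at 10. Suppose, as an assumption, 15 per arm in each gender and the same true effect in both. The chance that exactly one gender reaches p<0.05 is 2 × 0.396 × (1 − 0.396) = 0.478. Discordant results would be common without any difference between levels.

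**3. Counting the p-values.**

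- Per level: 5 seroresponse + 6 GMR + 4 thresholds × 6 days = 35.
- Four levels: 35 × 4 = 140. The by-race and by-gender immunogenicity tables are listed for the IEP only, so this is not doubled for the mITT population.
- Day 1 tests, before vaccination: (1 GMR + 4 thresholds) × 4 = 20.
- Seroresponse on Days 22, 29, 57 and 182: 4 × 4 = 16. The SAP addendum on removed tables reports a 4-fold rise in all subjects by the second time point and 100% in both groups thereafter, so Fisher's p = 1.
- Titer ≥40 on the same four days: 4 × 4 = 16. SAP 3.3 sets baselines below 15 to 15 for fold rise, so a 4-fold rise means at least 4 × 15 = 60. Universal response therefore forces 100% at ≥40, and again p = 1.
- Remaining: 140 − 20 − 16 − 16 = 88 at most. If the second time point means Day 8, fewer remain.

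**4. Chance of at least one p<0.05 with no arm effect.** The documents give no SD, visit correlation or subgroup split, so all of these are assumed.

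- The 20 post-vaccination GMR t-tests alone: 20 × 0.05 = 1.0 expected. Simulation with gender balanced and white subjects at 80% of one arm and 50% of the other gives a chance of at least one of 51%, 43% and 35% at visit correlations 0.5, 0.7 and 0.85.
- All 120 post-vaccination tests (140 − 20), simulated with log10 SD 0.4 to 0.6, correlation 0.3 to 0.9, three titer profiles and factor splits of 70:30 with 60:40, or 85:15 with 50:50: 1.3 to 1.75 expected, and a chance of at least one of 39% to 65%. In these runs the t-tests alone gave 30% to 58%, the low end at correlation 0.9.
- The 32 fixed tests hardly affect this. At 15 per arm, Fisher's true size is 0.06% at a 95% rate, so 32 × 0.0006 ≈ 0.02 expected. At rates of 50% to 90% its size is 0.55% to 1.7%, well under 5%.

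**5. What an interaction could detect.** With 30 per arm, SE = SD × √(sum of 1/n over the four cells). The detectable ratio of GMRs at 80% power is 10^(2.80 × SE), by normal approximation.

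- 50:50 split: √(4/15) = 0.516.
- 70:30 split in both arms: √(2/21 + 2/9) = 0.563.

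| Assumed log10 SD | 50:50 | 70:30 |
|---|---|---|
| 0.4 | 3.8-fold | 4.3-fold |
| 0.5 | 5.3-fold | 6.2-fold |
| 0.6 | 7.4-fold | 8.8-fold |

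**The case against.** The case for leaving the plan alone has several sound parts.

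- **The analyses are supportive.** The primary analysis is a single Day 22 comparison, no stated objective concerns effect modification by race or gender, and no decision rule uses a subgroup p-value. The plan is open that "no adjustment for multiplicity will be applied". This stands, and it keeps the severity low.
- **The nominal count overstates the exposure.** A reader might go from 140 tests at 0.05 to 140 × 0.05 = 7 expected false positives and 1 − 0.95^140 = 99.9% for at least one. The documents do not support that. At least 52 of the tests are pre-vaccination or fixed, most of the rest are conservative Fisher tests, and all are correlated.
- **The loss of adjustment is partly unavoidable.** Gender cannot be adjusted for within a single-gender subgroup, and the arms are matched on age and gender, which limits the effect of omitting those terms. What survives concerns race: matching does not involve race, so balance on age and gender within a race level is not assured.
- **Removing p-values does not remove the risk.** A t-based 95% CI for a GMR excludes 1 exactly when the matching t-test gives p<0.05. This stands, and is why the intervals need a descriptive label and a direct interaction estimate beside them.
- **An interaction would be weak and late.** Both points stand. SAP 8 already refers to high seroconversion in both groups and to models that would not fit, and the addendum on removed tables describes a decision taken after database lock.

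None of this answers the central gap: the planned output has no quantity that compares the arm effect between levels.

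**Conclusion.** The point holds at low severity. As written, SAP 6.4 yields unadjusted within-level p-values, 140 nominal and at most 88 informative, and no estimate of whether the arm effect differs by race or gender.

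With no true effect, the chance of at least one p<0.05 is roughly even, about 35% to 65%. That range rests wholly on assumed SDs, visit correlations and subgroup splits; the GMR tests alone fall to 30% at a visit correlation of 0.9. Any figure for subjects per arm per level, such as 15, is likewise an assumption.

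A reader might infer that chance findings are near certain, or that the trial's main conclusion is exposed. Neither follows: the first treats the tests as independent and exactly 5% in size, and the primary test does not depend on section 6.4.

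**What to change.** In SAP 6.4:

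- Remove the within-level p-values. Keep the estimates with 95% CIs and label them descriptive.
- From the Day 22 log10-titer model, report one arm-by-gender and one arm-by-race interaction, each as a ratio of GMRs with its 95% CI. The gender model has arm, age, gender and arm × gender. The race model has arm, age, gender, race group and arm × race group.
- State that power is low (detectable ratio of GMRs about 4- to 9-fold for an assumed log10 SD of 0.4 to 0.6 and splits from 50:50 to 70:30), and that a non-significant interaction does not show consistency across levels.
- If the analysis is added after data were seen, label it post hoc.

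Using titer rather than seroresponse avoids the fitting failure that SAP 8 reports for the logistic models.

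The cost is a short wording change, fewer p-value columns and two extra model terms, with no new data. The downside is wide interaction intervals, and the chance that some descriptive interval excludes 1 remains.

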7. SAFETY ANALYSES

7.1. Extent of Exposure

Vaccine administration data, including date/time of vaccination and injection site location, will be provided in a listing for all subjects in the exposed population.

All safety analyses will be based on the safety population.

7.2. Adverse Events

An AE is any untoward medical occurrence in a study participant, regardless of the suspected causal relationship with study vaccine. An AE can therefore be a new-onset symptom or disease, an exacerbation of a pre-existing symptom or disease, a new-onset laboratory abnormality considered by the Investigator to be clinically significant, a new-onset symptom or disease that occurs as a result of a protocol-specified procedure.

The reporting period for SAEs begins at the time of informed consent and continues for the duration of study participation. The reporting period for solicited AEs begins after study vaccine administration on Day 1 and continues through Day 8. The reporting period for unsolicited AEs begins after study vaccine administration on Day 1 and continues through Day 29.

Solicited AEs are assigned to two different categories of events, systemic and local, with the following pre-specified signs and symptoms:

1. Systemic events: fever with oral temperature ≥ 100.4 °F, chills, malaise, fatigue, headache, myalgia, arthralgia, and nausea
2. Local events: pain, redness, and swelling at the injection site

Solicited AEs from Day 1 through Day 8 will be recorded on the solicited AE electronic case report form (eCRF). Symptoms experienced on Day 8 and continuing beyond Day 8 will be recorded on the AE eCRF with a start date corresponding to the first date the symptom was continuously experienced through Day 8.

An unsolicited AE is defined as an AE that is spontaneously reported by the subject or discovered by the Investigator.

Adverse Event Dictionary

AEs will be coded using the MedDRA version 20.1. SOC, High Level Group Term (HLGT), High Level Term (HLT), PT, and Lowest Level Term (LLT) will be attached to the clinical database.

All solicited AEs will be summarized according to severity grading scales defined in Sections 6.2 and 9.5.1 of the protocol; these range from “mild” to “potentially life-threatening.”

The analyses of solicited AEs (categorized as systemic or local) will be tabulated by maximum severity and study arm. In addition, solicited AEs ongoing after 7 days post-injection will be also recorded as unsolicited AEs. Frequencies and percentages of subjects experiencing each solicited AE will be presented by maximum severity.

All the unsolicited AEs occurring during the study that occur during reporting periods will be recorded, regardless of their assessment of relatedness by the Investigator. The original verbatim terms used by the Investigator to identify AEs in the eCRF will be mapped to preferred terms using the MedDRA dictionary. The unsolicited AEs will then be grouped by MedDRA preferred terms into frequency tables according to SOC. All reported AEs, as well as AEs judged by the Investigator as at least possibly related to study vaccine, will be summarized by study arm, according to SOC and preferred term within SOC. When an unsolicited AE occurs more than once for a subject, the maximum severity and strongest relationship to the study arm will be counted. Only treatment-emergent AEs will be summarized, i.e., excluding those after a subject has given informed consent, but before vaccination. The selection of unsolicited AEs and their assignment to time intervals will be done by day of onset and not by days ongoing/persisting.

7.2.1. Adverse Event Severity

AEs (inclusive of all solicited and unsolicited AEs) are graded by the Investigator or designee as Grade 1 (mild), Grade 2 (moderate), Grade 3 (severe) or Grade 4 (potentially life-threatening) according to toxicity criteria specified in the study protocol (see Appendix B of study protocol). The severity grade of events for which the Investigator did not record severity will be categorized as “missing” for tabular summaries and data listings, and will be considered the least severe for the purposes of sorting for data presentation (will sort to the top).

7.2.2. Relationship of Adverse Events to Study Drug

AEs and SAEs are determined to be related or unrelated to study product by study Investigators or their designees. The Investigators or designees will evaluate the relatedness of an AE to vaccine treatment using three categories: Not Related, Possibly Related, and Probably Related. Related AEs are those for which the Investigator or designee answers “Possibly Related” or “Probably Related”. Events for which the Investigator or designee did not record relationship to study drug will be considered related to study drug for the purposes of analysis. Data listings will show relationship as missing in this case.

7.2.3. Serious Adverse Events

SAEs are those identified in the clinical database as serious by the Principal Investigator or designee. Further information on the definition of a SAE is provided in Section 6.1.4 of the study protocol.

7.2.4. Summaries of Adverse Events and Deaths

A single summary table of AEs will tabulate, by study arm, the number and percentage of subjects who had any (1) solicited or unsolicited AE, (2) solicited AE, (3) solicited systemic AE, (4) solicited local AE, (5) unsolicited AE, (6) treatment-related solicited or unsolicited AE, (7) solicited treatment-related AE, (8) solicited systemic treatment-related AE, (9) solicited local treatment-related AE, (10) unsolicited treatment-related AE, (11) SAE, (12) treatment-related SAE, (13) solicited or unsolicited AE leading to permanent discontinuation from the study, and (14) death during study.

Summaries (number and percent of subjects) of AEs will be provided by SOC and PT and study arm as follows:

- All AEs (inclusive of all solicited and unsolicited AEs)
- All unsolicited AEs
- Treatment-related unsolicited AEs
- AEs that caused permanent discontinuation from study,
- Unsolicited AEs by maximum severity grade,
- Treatment-related unsolicited AEs by maximum severity grade.

For subjects with multiple events, only one event will be counted in each summary. For data presentation, SOCs will be ordered alphabetically, with PT sorted by decreasing total frequency. Solicited AEs will be presented by decreasing total frequency. For summaries by maximum severity grade, only the event with the highest severity will be presented. For summaries by relatedness, only one event per relatedness category will be presented. Summaries will be provided by study arm and for the Safety Population.

In addition to the by-treatment summaries, data listings will be provided for the following:

- All unsolicited AEs
- All solicited events
- AEs leading to discontinuation from study
- SAEs
- Deaths

7.3. Safety Endpoints

The safety and tolerability endpoints include local and systemic post-injection solicited events and other AEs collected during the 7 days following the injection. Safety endpoints also include the occurrence of any unsolicited AEs through Day 29, and SAEs and AEs leading to withdrawal at any time during the study. All safety data will be tabulated according to study arm and at the time points of assessment.

7.3.1. Analysis Methods for Safety Endpoints

The number and percentage of subjects who experience a solicited AE recorded during Days 1 through 8 will be summarized according to maximum severity grade by study arm and decreasing total frequency. For subjects with multiple events of the same type, only the event of the highest severity will be counted in each summary. Events with missing severity grades will be handled according to Section 7.1.1. A Fisher's exact test will be used to compare the frequency of the corresponding solicited event between the two groups. The 95% CI for the subject percentages will be calculated using the Wilson method. This summary will be repeated for treatment-related solicited AEs and solicited AEs during Days 1 through 8 of at least severe (Grade 3) severity or higher.

Day of onset post-injection will be summarized with descriptive statistics for each type of solicited AE by study arm. The median and its 95% CI will be estimated by Kaplan-Meier analysis. The log-rank test will be used to compare day of onset between the two study arms. This summary will be repeated for treatment-related solicited AEs.

The number of days a subject experiences each solicited AE will be summarized by descriptive statistics (number of subjects with each solicited AE, mean, median, minimum and maximum) by study arm. The days may not be consecutive. The 95% CI of the mean will be based on t-statistics assuming a normal distribution. The 95% CI of the median will be a distribution-free estimate based on order statistics. A Wilcoxon rank sum test on the number of days of symptoms will be used to compare both groups. This summary will be repeated for treatment-related solicited AEs.

The percentage of subjects reporting solicited AEs will also be summarized for each event category and sign and/or symptom by study arm and day on study.

A summary of the number and percentage of subjects who experience an unsolicited AE during Days 1 through 29 by SOC and PT will be presented. Similarly, a summary of the number and percentage of subjects who experience a treatment-related AE during Days 1 through 29 by SOC and PT will be provided.

In addition, a summary of the number and percentage of subjects who experience an SAE during Days 1 through 182 by SOC and PT will be presented. Similarly, a summary of the number and percentage of subjects who experience a treatment-related SAE during Days 1 through 182 by SOC and PT will be provided.

